3.3 Study Measures

	SCREEN A	SCREEN B	INITIAL CALL	SURVEY 1	BASELINE	SURVEY 2	INTERVENTION	SURVEY 3	FMRI
Measures				Day 0	Day 1 – 15	Day 15	Day 15 – 45	Day 45	
File submissions									
Vaccination card (photo)		X							
Location tracking (timeline export)		X				X			
Urine cotinine test (photo)				X					X
Receipts (photos)							20X		
Screening and Covariates									

Eligibility screening	X	X						
Smoking behavior survey			X		X		X	1 item
Nicotine dependence survey (FTND)			X		X		X	X
Smoking habits survey			X				X	
Smoking cessation intentions survey			X				X	
Smoking info exposure questionnaire			X		X		X	
Smoking beliefs survey			X				X	
Smoking attitudes survey			X				X	
Social smoking norms survey			X				X	
Smoking motivation survey			X					
Tobacco policy support questionnaire			X				X	
Social interactions & smoking survey					X (weekly survey)	4X (weekly survey)		
Demographics survey			X					
Stressful Life Experiences Inventory					X			
Microaggression s survey			X		X (weekly survey)	4X (weekly survey)	X	
Purpose in life survey			X	1 item daily		1 item daily		
Smoker self-concept survey			X				X	

Perceived stress scale		X				X	
CES-D Depression scale			X			X	
Code switching survey			X			X	
Mindfulness (MAAS)							X
Impulsiveness (BIS-11)							X
Alcohol consumption							X
Outcomes							
Cigarette consumption-self-report		X		X		X	
EMA text surveys - smoking and craving			X		X		
Cue reactivity task				X		X	X

3.4 Study Endpoints

3.4.1 Primary Study Endpoint

The primary endpoints will be cigarette smoking and craving at the end of the intervention period, measured through EMA multiple times daily. The primary endpoints for the fMRI scan session will be measured through fMRI scanning (brain activity).

3.4.2 Secondary Study Endpoints

4 Study Population and Duration of Participation

The target population is current smokers, ages 21-65, who have smoked at least 5 cigarettes a day for the past 6 months, are smartphone users, and live in PA/NJ/DE.

4.1 Duration of Study Participation

The target behaviors (smoking frequency, cravings for cigarettes) will be assessed for an approximately 2 week baseline period and for an approximately 4 week intervention period. Thus, total study participation is expected to be approximately 6 weeks of active participation, with possible breaks in between the baseline and intervention periods. Total duration of

participation will thus be approximately 2 months, with some exceptions (such as pauses in active participation because of the University's special winter vacation, or as requested by participants due to external constraints). A subset of participants will be invited to complete an optional fMRI scan after their final online session; flexibility will be allowed in the timing of the scan session, which can be as long as 6 months after the final online session. This subset of participants will participate for a longer duration (total duration of participation can be up to 8 months [2 months of active participation, with a scan session up to 6 months later]).

4.2 Total Number of Subjects and Sites

Our initial recruitment plan specified that "Recruitment will end when approximately 400 participants have been enrolled. It is expected that 400 enrolled participants will produce 180 evaluable subjects after attrition and data issues. Penn is the only site." See 6.1 for final plan, adjusting for COVID and other constraints.

4.3 Inclusion Criteria

- Be between the ages of 21-65
- Smoke at least 5 cigarettes a day for the past 6 months
- Own an iPhone or Android smartphone that can be used on a daily basis
- Be residents of Pennsylvania, New Jersey, or Delaware
- Read and speak English fluently
- Fully vaccinated against COVID-19

4.4 Exclusion Criteria

- Current enrollment or plans to enroll in a smoking cessation program in the next 3 months
- Plan to use nicotine substitutes or smoking cessation treatments in the next 3 months
- Pregnancy
- Refusal to install Google Maps or LifeData applications on mobile phone
- Inability or refusal to upload Google Timeline data after receiving instructions and guidance during or after the initial intake call
- During the first two weeks of the study, failure to complete the study tasks (response to at least 75% of the brief EMA survey questions)
- Urine cotinine testing at Session 1 indicates a non-smoker level of cotinine
- The phones of potential participants will be assessed by trained recruiters during a phone call used to invite eligible participants who completed Screen A to participate in the study. Specifically, recruiters will assess whether phones' functionality allows easy reception and sending of text messages, the use of the geolocation tracking and LifeData applications and whether phones have an adequate battery life to allow participants to fulfill study requirements.
- Inability to provide informed consent or complete any of the study tasks as determined by the Principal Investigator and/or Study Physician.
- Any physical or visual impairment that may prevent the individual from using a computer keyboard or completing any study tasks.

Additional criteria for fMRI component:

- Demonstrate urine cotinine concentration below 200 ng/mL at scanning session
- Currently or recently (within the last 5 years) receiving medical treatment for substance abuse (e.g., alcohol, opioids, cocaine, marijuana, or stimulants). Treatment of substance use disorders that occurred greater than 5 years prior to study participation is acceptable if participants are in stable condition

- Report consuming any of the following drugs within the past two weeks or indicate plans to do so within the coming 6 weeks during the screening call: Benzodiazepines, Amphetamines, Methamphetamines, Cocaine, MDMA, Methadone, Barbiturates, PCP, Heroin, Oxycodone, Opiates (e.g., morphine, heroin), Buprenorphine
- Test positive for any of the above drugs at the scan appointment
- Schizophrenia or psychosis, regardless of treatment status.
- History of stroke or other neurological disorder likely to affect cognition
- Psychiatric hospitalization within the past year
- Propensity to experience claustrophobia
- Ferromagnetic metal in the body, including anything that might set off a metal detector. Examples include bullet shrapnel, metal shavings (e.g., from welding without protection), or any implant that may be attracted to or damaged by magnets. Dental fillings are generally acceptable.
 - Metal in the body of an unverifiable origin.
 - Non-removable piercings.
 - Non-removable retainers or other dental work not compatible with fMRI.
 - Any orthopedic implant above the neck.
 - Due to constraints of the fMRI scanner, participants whose weight exceeds 350 pounds also will be excluded. The size of the scanner will be discussed with all participants during the consent addendum procedure.
 - Any medical condition or concomitant medication that could compromise participant safety or treatment, as determined by the Principal Investigator and/or Study Physician.
 - Unable to schedule a scan within 6 months after completing the third Online Session

4.5 *Subject Recruitment*

Direct recruitment may occur through newsletters, fliers, online ads/posts (e.g., Craigslist, Facebook, Instagram), newspaper listings, and/or ads on TV (or streaming media services). Recruitment materials may be posted by the study team or by BuildClinical. We will also collaborate with another smoking research group at the University of Pennsylvania which has IRB approval for passing on contact information of interested participants to other research teams. Only participants who have indicated that they are interested in being contacted for future studies will be approached. Upon contact, it will be made clear to participants that there is a possibility for them to participate in the study and they will be provided with IRB-approved recruitment materials such as flyers, text, and/or oral information about the study, depending on the mode of contact. All recruitment material will include links (e.g., URLs, QR codes) directing potential participants to the screening survey (Screen A). The study email address and/or phone number may be included, depending on the recruitment medium. Interested individuals will complete Screen A on their own device at a time that is convenient to them.

Vulnerable Populations:

Not applicable

5 *Study Procedures*

5.1 Screening

5.1.1 Screen A

Those who express interest in the study by reacting to the recruitment efforts will be directed towards an online screening survey (Screen A) where they answer questions relevant to their eligibility for the study and provide their contact information. Screen A will also include a question that asks about the participants' interest in receiving information on opportunities to participate in other remote and/or in-person studies.

- Screen A will be administered online via RedCap or BuildClinical and is estimated to take less than 5 minutes to complete.
- [Note: If one's screening survey responses indicate that they are not eligible to participate in this study, they will receive an email informing them of this.]
- [Note: If one's screening survey responses indicate that they are interested in, and potentially eligible for, the in-person version of this study (protocol 822815), they may be provided a link to that study's screening survey and will be filtered through the process outlined in the 822815 protocol. If they are then found to be ineligible for the in-person study, they may be redirected to this remote study.]

Survey respondents who are potentially eligible to participate in the remote study will be emailed and/or texted a link to Calendly (appointment booking system) to allow participants to sign up for a time for an initial phone call to find out more about the study.

5.1.2 Initial Call

During the initial call, participants will be informed about the study, including the risks and benefits of participation, and will be given the opportunity to ask questions. Eligibility criteria will be confirmed on this call as needed.

- The initial call will be conducted over the phone (Google Voice) and is expected to take approximately 30 minutes. The researcher conducting the call will enter participant responses into RedCap.

At the end of the initial call, potential participants who are still eligible and interested will be invited via email to complete Screen B at a time of their choosing within 1 month of the initial call.

5.1.3 Screen B

Screen B begins with a RedCap e-consent form for the screening survey, which will guide potential participants to provide their shipping address and submit a picture of their COVID-19 vaccination card. The instructions will then guide them through downloading and/or setting up Google Maps on their phone, then exporting and uploading their Google timeline (location history) data.

- Screen B will be administered online using RedCap and Qualtrics (with Penn Box as a back-up method for submitting location data, if needed). The screen is expected to take 5 - 15 minutes of active participation, which excludes the passive time (when participants are not asked to do anything) while Google is compiling the participants Timeline data for export.
- Potential participants who have difficulty with the Google Maps set-up or timeline export will be able to sign up for an additional phone/video call at a later time to receive help from a researcher.

Researchers will then confirm A) that potential participants live in the study area (PA, NJ, or DE) using the uploaded timeline data and shipping address and B) that the potential participant is fully vaccinated against COVID-19, both of which are required to be eligible to participate in this study.

- [Note: Those who are unable/unwilling to complete any component of Screen B, live outside of the specified study area, or are not fully vaccinated will be ineligible for this study and will not be given the opportunity to enroll. The team will inform them of their ineligibility, delete their geolocation data, and provide them with instructions for turning off Google Timeline and uninstalling Google Maps.]
- [Note: If potential or enrolled participants are no longer interested in enrolling in the study at any point during or after the Google Maps set up, they will be provided with instructions for turning off Google Timeline and uninstalling the app.]

5.1.4 Mailing Materials

Eligible individuals will then be mailed a box containing study materials, including items such as the urine cotinine test, KN95/KF94 or N95 masks, and a Greenphire Clincard. Upon receipt of the study materials, participants will be given instructions to enroll in the study and begin their participation by completing Session 1.

5.2 Study Observational Phase

5.2.1 Online Session 1 (S1)

In Session 1, participants will read through the consent form and provide electronic consent via RedCap to participate in the full study and provide information required for payment (legal name, date of birth, and Social Security number). Participants will then follow the survey instructions to: complete physiological measurements (urine cotinine) and self-report measures; receive instructions for the Baseline period EMA task and answer questions assessing their comprehension of the task; and install, set up, and practice using RealLife Exp (the EMA app) on their smartphone.

- Session 1 will be administered over RedCap and Qualtrics, and is expected to take 30-60 minutes.
- If a participant's urine cotinine test result is not above the threshold required for eligibility, the participant will be excluded from continuing in the study.

5.2.2 Observational Phase

The baseline period will begin after completion of Session 1, and will last for 14 days. During the baseline period, participants will complete EMA and location tracking.

- Participants will be excluded for non-compliance at the end of the baseline period if they have not responded to at least 75% of EMA prompts.
- Following the baseline period, participants will be assigned to an experimental condition.

5.3 Study Interventional Phase

5.3.1 Online Session 2

Participants will be invited to complete Session 2 online after completing the baseline observational period. They are encouraged to complete the session within 4 days and no longer than 1 week (with possibility for exceptions at experimenters discretion) after receiving the invitation. Participants complete self-report measures; an image rating task; geolocation data

export and upload; EMA setup and practice; and instructions and practice for the Intervention tasks.

- Session 2 will be administered over Qualtrics, and is expected to take 30-60 minutes.

5.3.2 Intervention Phase

The Intervention Period will begin after completion of Session 2. During the 4 week intervention period, all participants will complete EMA, location tracking, and weekly surveys. The specific study-related tasks participants are asked to carry out during the intervention period depends on which experimental group they have been randomized to. The two experimental groups (tobacco retailer and nontobacco retailer) will be asked to enter a specific store 5 times per week for 4 weeks. The control group will not be asked to enter a store.

5.3.3 Online Session 3

Following the Intervention Period, participants will be invited to complete Session 3 online, which they are encouraged to complete within 4 days and no longer than 1 week (with possibility for exceptions at experimenters' discretion) of receiving the invitation. Participants will complete surveys; an image rating task; and geolocation data export and upload. At the end of the session, participants will be instructed on how to uninstall study-related smartphone applications and turn off smartphone location tracking, as desired. If not interested in and/or potentially eligible for the scan session, participants will also be provided with a debriefing form, which includes details about the study procedure and research goals, and may request a phone call or video call to go over the content of the form. They will be provided with a Quit Resources document, which contains information about services that provide smoking cessation assistance. For participants interested in being screened for the scan, debriefing and provision of the quit resources document will occur after the scan or as soon as scan session ineligibility is determined.

5.3.4 Optional fMRI session

- fMRI Screening: Participants who complete Session 3 and are potentially eligible to participate in the optional, in-person fMRI session (as determined by self-report questions in previous screening surveys and online sessions) may be informed of the opportunity and invited to complete an additional, optional fMRI screening survey. The fMRI screen will contain questions relevant to their eligibility for the in-person component of the study.
- fMRI session: This is a 2 hour session. After confirming that the participant meets any COVID-19 screening requirements (e.g., symptom screen, temperature check), during the in-person session, researchers will review the consent addendum document with participants. After providing written informed consent, participants will complete any required forms (e.g., W-2, additional metal screen) and provide a urine sample to confirm eligibility. Eligible participants will receive safety and task-related instructions/training before completing the fMRI scan. During the 1-hour scan component of the session, participants will complete an image rating task. Depending on time of arrival, participants may be asked to complete a brief survey before and/or after the scan.

5.4 Unscheduled Visits

At the end of Screen B and at the end of each online session, participants will be invited to provide feedback on their experience in the study to that point, via an open answer text box. We may follow up with participants by email or phone to clarify feedback as needed.

5.5 Subject Withdrawal and Exclusion

Subjects may withdraw from the study at any time without penalty. Participation in the study may also be stopped at the discretion of the Investigator for lack of adherence to study instructions, or if the Investigator determines exclusion is best for subject safety or health. Specific exclusion criteria are detailed below.

ONLINE SESSION 1: If a participant's cotinine test result is not above the threshold required for eligibility, the participant will be excluded from continuing in the study. Participants who are found to be ineligible during Session 1 (e.g. due to the results of their cotinine tests) will be paid \$75 on their ClinCard for the tasks they completed but will be excluded from continuing their participation in this study.

BASELINE PERIOD: If participants are excluded (e.g., for responding to less than 75% of EMA) or withdraw during the baseline or intervention periods, they will be issued payment on their ClinCard at the rate of \$4 per day that they responded to at least 75% of EMA surveys.

INTERVENTION PERIOD: Participants in the experimental group who discontinue participation during the intervention period will also be paid according to the standard schedule for EMA compliance (\$4/day at 75% or higher) and receipt submission (\$5 per verified daily receipt). Participants who do not complete required study tasks during the intervention (e.g., submitting fewer than 20 store receipts, EMA compliance below 75%) will not receive the study completion bonus.

Withdrawn and excluded participants who complete an optional offboarding call will be compensated for their time at a rate of \$15/hour.

FMRI SESSION: Participants who must be excluded or asked to reschedule by the experimenter after arriving for the in-person session will be paid \$15 for their time via their ClinCard or petty cash.

In the event of lateness, technical issues, unexpected ineligibility for specific components of the protocol, or any reason that a participant is unable to complete a specific portion of the protocol, the study team may have them complete all other portions for which they are eligible to complete at the experimenters discretion and pay them the standard compensation rate.

5.5.1 Data Collection and Follow-up for Withdrawn Subjects

All withdrawn and excluded participants are sent instructions to turn off location tracking & delete the RealLife Exp app. They are also informed that they can contact us to schedule an optional offboarding call if they would like assistance with this process. This optional offboarding call will be compensated for their time at a rate of \$15/hour. These participants will also be sent a link to submit geolocation data for a final time for an additional \$5 payment (estimated 20 minutes at a rate of \$15/hour).

5.6 Early Termination Visits

All withdrawn and excluded participants are sent instructions to turn off location tracking & delete the RealLife Exp app. They are also informed that they can contact us to schedule an optional offboarding call if they would like assistance with this process. This optional offboarding call will be

compensated for their time at a rate of \$15/hour. These participants will also be sent a link to submit geolocation data for a final time for an additional \$5 payment (estimated 20 minutes at a rate of \$15/hour).

5.7 Safety Evaluation

We evaluated safety according to our original plan:

1. After collection of 60 participants (approximately 20 in each group) and 120 participants (approximately 40 in each group), we will use EMA data to identify:
 - a. The distribution (histogram) of each participant's daily cigarette consumption (cig/day) during the baseline period ($b0$)
 - i. Including each ppt's mean baseline consumption ($cigs/day_{b0}$) & standard deviation (SD_{b0})
 - b. The distribution (histogram) of each participant's daily cigarette consumption (cig/day) during weeks 3 and 4 of the intervention period ($i3-4$)
 - i. Including each ppt's mean consumption ($cigs/day_{i3-4}$) & standard deviation (SD_{i3-4}) for intervention weeks 3 and 4
2. Participants will be identified as "increased smokers" if their average daily cigarette consumption during the final 2 weeks of the intervention period is more than 3 standard deviations above their baseline mean
 - a. Increased smokers: $cigs/day_{i3-4} > (cigs/day_{i3-4} + 3SD)$
3. If the number of "increased smokers" in the Tobacco retailer condition is significantly ($p \leq .01$) greater than the number of "increased smokers" in the control condition, this will trigger the study team to reconvene for a reassessment with members of the study team, the Primary Investigator, the Co-Investigators who have expertise in tobacco research, and the external stakeholders. This may result in the termination of this arm of the study and reassignment of future participants to the other two groups. Additionally, as part of this review, we will reach out to the participants in all conditions who met the criteria for an "increased smoker" to offer additional counseling on smoking cessation resources. The group will further make a plan to mitigate future risks to participants.

6 Statistical Plan

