3.1 General Design

Study Type: Interventional

Primary Purpose: Other

Study Phase: N/A

Interventional Study Model: Parallel Assignment

Random assignment of retail environment (tobacco retailer, non-tobacco retailer, no store) to visit 5 times per week during the 4-week intervention period

Number of Arms: 3

Masking: Single (Investigator)

Investigator will not know the condition assignment of individual participants unless reassessment is triggered by the stopping rule.

Allocation: Randomized

Enrollment: 343 [Actual]

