6.3.3 Interim Analysis

At two time points during data collection, we will assess whether the study is producing unexpectedly positive or negative effects on participant outcomes. After collection of 60 participants (approximately 20 in each group) and 120 participants (approximately 40 in each group), we will test whether individuals in the Tobacco retailer condition have significantly changed the number of cigarettes that they smoke per day (as described in 5.7). If this group of participants changes their cigarette consumption by a clinically significant level, we will stop assigning participants to that group and assign all further participants equally to the other groups.

7 Safety and Adverse Events

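### Tobacco retailer safety rule: formula 2a in 5.7 cannot be met as printed, and 6.3.3 gives the same looks a different trigger and action

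*Combined protocol and SAP*

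**What the plan says.** Section 5.7 (Safety Evaluation) sets two looks, after 60 and 120 participants. Items 1a and 1b define each participant's mean and SD of cigarettes per day twice: at baseline (subscript b0) and in intervention weeks 3 and 4 (subscript i3-4). Item 2 calls a participant an increased smoker if the weeks 3-4 mean "is more than 3 standard deviations above their baseline mean". Formula 2a then writes this as "cigs/day_{i3-4} > (cigs/day_{i3-4} + 3SD", with a closing bracket. Item 3 compares the number of increased smokers in the Tobacco retailer arm with the number in Control. If the Tobacco retailer count is significantly greater at p ≤ .01, "this will trigger the study team to reconvene for a reassessment". On the arm itself, item 3 says "This may result in the termination of this arm of the study".

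Section 6.3.3 (Interim Analysis) covers the same two looks. It opens with "we will assess whether the study is producing unexpectedly positive or negative effects on participant outcomes". It tests whether people in the Tobacco retailer condition "have significantly changed the number of cigarettes that they smoke per day (as described in 5.7" (the bracket closes there). Its decision sentence is "If this group of participants changes their cigarette consumption by a clinically significant level, we will stop assigning participants to that group".

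Section 3.1 (General Design) says that the investigator stays blind to individual assignments "unless reassessment is triggered by the stopping rule".

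**The concern.** This is the only stopping rule in the plan, and it protects participants who are sent into tobacco retailers. The criterion should be computable, and it should be stated once. As printed, the formula flags nobody, and the two sections lead to different decisions from the same data. Section 5.7 also says that safety was evaluated according to the plan it then prints. A reader of the results therefore cannot tell from the document which definition, trigger and action were applied at the two looks.

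**Working it through.** There is no stated figure to reproduce. The check is one line of algebra, a short simulation and a comparison of two sections.

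**Step 1: formula 2a.** Write x for the weeks 3-4 mean and b for the baseline mean.

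- As printed: x > x + 3SD. Subtracting x from both sides gives 0 > 3SD, which is false for every SD ≥ 0. The missing subscript on SD makes no difference.
- As worded in item 2: x > b + 3SD. This can be met.

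A simulation illustrates the difference. The inputs are assumptions, not figures from the plan: baseline mean 15 cigarettes per day, within-person SD 4, 14 days in each period, and 20,000 simulated participants per scenario.

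| Rise in cigarettes per day | Flagged by 2a as printed | Flagged with `cigs/day_b0 + 3*SD_b0` |
|---|---|---|
| 0 | 0% | 0% |
| 5 | 0% | 0.5% |
| 10 | 0% | 27% |
| 15 | 0% | 87.5% |
| 20 | 0% | 99.8% |

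Taken literally, 2a makes every comparison 0 against 0, so the p ≤ .01 trigger could not be reached at any look. With the baseline mean restored, the rule works and agrees with item 2. A distance above the baseline mean is most naturally measured in baseline SDs, so `SD_b0` also settles the missing subscript.

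**Step 2: 5.7 against 6.3.3, same looks and same arm.**

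| | 5.7 | 6.3.3 |
|---|---|---|
| Quantity | Number of increased smokers | Change in the group's consumption |
| Comparator | Control | None in the decision sentence |
| Direction | Increases only | Either |
| Threshold | p ≤ .01 | Clinical significance, not defined |
| Action | Reassessment, which may end the arm | Assignment to the arm stops |

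**Step 3: does the difference matter for a decision?** Suppose that smoking in the Tobacco retailer arm falls by a clinically important amount and no participant there is an increased smoker. Under 6.3.3's words, assignment to the arm stops. Under 5.7, a Tobacco retailer count of 0 cannot exceed any Control count, so nothing is triggered. The two sections then give opposite instructions.

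**The case against.** **The formula is only a typographical slip.** Item 2 states the rule clearly in words, both sets of symbols are defined just above it, and nobody could sensibly apply x > x + 3SD. Subscripts are also easily misread when text is taken from a PDF. This largely stands. It limits the formula point to a correction of the record, and a look at the source PDF would show whether even that is needed.

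**Section 6.3.3 only summarises 5.7.** It points to 5.7 for its test, so its reference to clinical significance could be shorthand for 5.7's criterion. On that reading much of the conflict over threshold and direction goes away. The cross-reference, however, sits in the sentence about the test. The next sentence sets its own condition and a mandatory action, and a stop that will happen is not the same as a reassessment that may lead to one.

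**A reader might infer that a fall in smoking could never meet 5.7's trigger.** The documents do not support that, because 5.7 counts individuals while 6.3.3 speaks of the group. Take an assumed within-person SD of 1 and 20 participants per arm. Let 7 in the Tobacco retailer arm rise by 4 cigarettes per day (more than 3 SD) and 13 fall by 8. The mean change is (7 × 4 − 13 × 8)/20 = −76/20 = −3.8. Yet 7 increased smokers against 0 in Control gives one-sided p = .0042 by Fisher's exact test (an assumed choice, since 5.7 names no test), which meets 5.7's trigger. An overall fall does not in itself meet the trigger, but it does not rule it out.

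**A reader might also take it as settled that 5.7 governs.** Only 3.1, with its reference to reassessment, clearly supports 5.7's action. Section 7.2 sends the smoking data to 5.7 but is silent on action. Section 7.4.3 describes a stopping rule against unexpected risk, but its preceding sentence speaks of unexpectedly large effects without giving a direction. The sponsor has to confirm which rule was used.

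**Conclusion.** Both parts hold, at minor severity. Formula 2a as printed cannot be met and contradicts item 2. Section 6.3.3 is inconsistent with 5.7 on trigger and action, and the cross-reference does not reconcile the action.

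The consequence is confined to the accuracy of the safety record. It would be tempting to conclude that monitoring was inoperative, but nothing in the documents shows that the printed formula was the one computed. The looks are past and enrollment is final. Section 6.1 reports 107 participants randomized to the Tobacco retailer condition and mentions no early closure of that arm. The mixed models in 6.3.2 do not use the rule, so the primary analyses are unaffected.

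The conclusion assumes that the subscripts were read correctly from the PDF. If the source shows the baseline mean on the right-hand side, the formula point falls away and the conflict between 5.7 and 6.3.3 remains.

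**What to change.** 1. Check 2a against the source file and print it as `cigs/day_i3-4 > (cigs/day_b0 + 3*SD_b0)`.
2. Have the sponsor confirm which trigger and action were applied at the 60- and 120-participant looks. If 5.7's rule was used, rewrite 6.3.3 to repeat it: an excess of increased smokers over Control at p ≤ .01, leading to a reassessment that may end the arm. If another rule was used, say so rather than overwrite it.
3. Report, for each look, the definition of an increased smoker, the statistical test used and the outcome.
4. Re-tabulate increased smokers by arm from the EMA data already held only if the baseline rule was not the one applied.

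The cost is two wording corrections and a short reporting statement, plus a small tabulation in the one case under item 4. No new data are needed.
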